## 4.2 EXCLUSION CRITERIA

Participants who meet any of the following criteria will *not* be eligible for this study:

1. Current malignancy requiring recent surgery, ongoing chemotherapy, or radiation.
2. Transplant of another organ.
3. Current drug or alcohol dependency.
4. Any medical condition that in the opinion of the principal investigator would interfere with safe completion of the trial.
5. Inability to comply with the study visit schedule and required assessments.

## 4.3 PREMATURE TERMINATION OF A PARTICIPANT FROM THE STUDY

**Withdrawal of consent.** Participants who withdraw consent for further follow-up.

**Investigator decision.** The principal investigator may choose to withdraw a participant from the study for any reason.

**Failure to return.** Participants who do not return for visits and who do not respond to repeated attempts by the site staff to have them return will be considered *lost to follow-up*.

Participants who prematurely terminate from the study will not be replaced.

## 5. STUDY MEDICATIONS

### 5.1 INVESTIGATIONAL MEDICATION

This section left intentionally blank.

## 5.2 CONCOMITANT MEDICATIONS

All immunosuppressive medications and any concomitant medications taken within 30 days prior to enrollment and to each annual visit will be documented at each visit. There are no prohibited medications.

## 6. STUDY PROCEDURES

Study procedures will be limited to yearly venipuncture and urine for clinical labs and mechanistic sample collection. A stool sample will also be acquired yearly for mechanistic purposes.

### 6.1 VISIT WINDOWS

#### 6.1.1 Scheduled Visits

Appendix 1 presents the schedule of events for this trial. Visit 0 must occur within 60 days of enrollment. All other scheduled study visits must occur within  $\pm$ 60 days of the scheduled time point listed in Appendix 1.

## 6.2 GENERAL ASSESSMENTS

### Recipient

- Informed consent
- Medical and demographic history including solid organ transplant specifics, any induction regimens, history of rejection and immunosuppression medication use since transplant:
  - For participants who previously participated in an ITN study, the participant ID and site ID (if separate) will be collected on the ALLTOL eCRF. The participant ID will be obtained by asking the ALLTOL participant for their previous ITN study participant ID and clinical study site.
- Contact information for local physician providing regular follow-up care for the kidney or liver transplant. Local care providers will be notified of any critical clinical information that may indicate allograft dysfunction. This process is further outlined in the MOP.
- Inclusion/Exclusion Criteria
- HLA and blood typing (if available)
- Change in adverse events and concomitant medications
- Development of clinical outcomes of interest, which include incidence of diabetes and/or any biliary complications

- If there is a 25% increase in the value(s) collected during the scheduled annual visit compared to the participant's baseline value, collect all liver function tests (for liver transplant recipients) or all serum creatinine levels (for kidney transplant recipients) since the last visit
- All biopsies
- All rejection episodes, including acute rejection, chronic rejection, antibody mediated rejection, and interstitial fibrosis and tubular atrophy rejection episodes

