### **7.1.2. Assessment Time Windows**

Visit 0 must occur within 60 days of enrollment. Each subsequent visit must occur yearly with a +/- 60-day window.

All data will be included in analyses, regardless of time of assessment.

Furthermore, clinical data and mechanistic specimens that have already been collected from enrolled subjects from previous ITN study participation may be used to supplement the ALLTOL specimens and data, as needed.

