### **7.2.1. Computation of the Primary Endpoint**

Normal and stable allograft function is defined as liver function tests (ALT, GGT) that have not increased more than 50% above the participant's baseline values for liver transplant recipients OR serum creatinine that has not increased more than 25% above the participant's baseline value for kidney transplant recipients.

For participants with study data that suggests the loss of operational tolerance according to the criteria in Section 7.2, the Primary Endpoint Adjudication Committee will review each case to determine if there were any potential confounding factors that may have impacted the participant's results. This committee will be comprised of the Study Protocol Chair, NIH Medical Monitor, a subject matter expert, and statistician. The following information will be presented to the committee in a blinded fashion (void of all ID and site information):

- a. Demographic and baseline characteristics (age at study entry, race, sex, ethnicity, organ type, transplant indication, age at transplant, transplant date, time from transplant, donor type, previous ITN study (Y/N), date off IS, time off IS).
- b. ALT and GGT lab values presented over time graphically for liver recipients OR creatinine values presented over time graphically for kidney recipients. A listing of each relevant lab value will also be included.
- c. All IS medication usage
- d. Any rejection event information
- e. Biliary complications or new diabetes diagnosis.

Additional information can be requested by the committee.

The committee will make a determination of each participant's tolerance status for participants with study data that suggests the loss of operational tolerance according to the criteria defined in section 7.2. The determination of the cases reviewed above will be recorded and signed off by the protocol chair and medical monitor.

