### **7.2.2. Primary Analysis of the Primary Endpoint**

The primary endpoint will be analyzed using Kaplan-Meier survival estimates and associated two-sided 95% confidence interval, using a delayed-entry model controlling for left-truncation of survival times through adjusting for the time from achieving operational tolerance to the time of study enrollment.

A participant will be considered to have lost operational tolerance if they experience rejection, have loss of stable allograft function (in the absence of confounding factors), or restart immunosuppression. The date of loss of operational tolerance (end date of operational tolerance) will be the first date on which the subject meets any of the criteria for loss of operational tolerance. Specifically,

- If tolerance is lost due to rejection, the date will equal the date of the biopsy.
- If tolerance is lost due to restarting immunosuppression, the date will equal the date of the first immunosuppression medication dosage.
- If tolerance is lost due to abnormal allograft function, the date will equal the first recorded abnormal lab date.

The time to loss of operational tolerance for all participants will be evaluated relative to time zero. Time zero will be considered 52 weeks from the participant's last documented dose of immunosuppression and in the absence of rejection or evidence for loss of normal and stable graft function since that last dose. If the exact date of the last dose is not known, the date will be imputed to the 15th of the month when the day is missing, and July 1st when both day and month are missing. The year must be known.

$$\begin{aligned} & \text{time to loss of operational tolerance} \\ & \quad = \text{end date of operational tolerance} - \text{start date of operational tolerance} \end{aligned}$$

Subjects lost to death, voluntary withdrawal or lost to follow-up will be censored at the time of occurrence of these events. Subjects who were followed until study closure (24MAR2020) without losing tolerance will be censored at the time of their most recent data point.

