## 7.4. Examination of Subgroups

In addition, the following subset analyses will be performed on all study endpoints where the data permits:

- a. Allograft type (liver vs. kidney)
- b. Previous ITN study participation vs. non-ITN study referral

All subgroup analyses will be descriptive in nature.

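### The 25% retrieval trigger lets between-visit labs add functional-loss candidates in liver recipients, but in kidney recipients it essentially only back-dates losses, so the two descriptive curves rest on different effective rules

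*Protocol*

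**What the plan says.** **Retrieval.** Protocol 6.2, repeated in Appendix 1 footnote 6, sets one trigger for both organs: "If there is a 25% increase in the value(s) collected during the scheduled annual visit" over the participant's baseline. When it fires, the site must "collect all liver function tests (for liver transplant recipients) or all serum creatinine levels (for kidney transplant recipients) since the last visit".

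**Loss thresholds.** SAP 7.2.1, in line with the protocol's Study Definitions, defines stable function as "liver function tests (ALT, GGT) that have not increased more than 50% above" baseline in liver recipients, and "serum creatinine that has not increased more than 25% above" baseline in kidney recipients.

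**Use of retrieved values.** SAP 7.1.2 states: "All data will be included in analyses, regardless of time of assessment". For a loss through abnormal function, SAP 7.2.2 says "the date will equal the first recorded abnormal lab date".

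**Adjudication.** Values affected by confounding factors do not count towards the endpoint. Cases whose data suggest loss go to the Primary Endpoint Adjudication Committee (SAP 7.2.1).

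**Organ subsets.** Protocol 3.3.1 and 9.1 and SAP 7.4 plan liver and kidney subsets on all endpoints. SAP 7.4 makes them descriptive and subject to the data permitting. Protocol 1.1 names the effect of allograft type on maintenance of tolerance among the questions the cohort should inform.

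SAP 7.2.3, the heading for sensitivity analyses of the primary endpoint, has no text beneath it. SAP section 10 does not mention the trigger.

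**The concern.** A common trigger looks even-handed, but its effect depends on where it sits relative to each organ's threshold. In liver there is a gap between trigger and threshold, and within that gap retrieval can turn a participant with no qualifying annual value into a candidate for loss. In kidney there is essentially no gap. Retrieval therefore changes event counts in liver and, for the most part, only event dates in kidney.

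The extra liver candidates also depend on how often the local physician tests, which the protocol does not set. Two liver recipients with the same graft behaviour can differ in their chance of being counted simply because one is tested more often.

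At stake is the reading of the laboratory component when the liver and kidney curves are set side by side. Rejection episodes, biopsies and immunosuppressant use are collected in both organs without this trigger and are not affected.

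**Working it through.** The plan gives no event rate, power or sample-size calculation, so there is no figure of its own to reproduce. The direction follows from the thresholds alone; the size needs assumptions.

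**Step 1: the thresholds side by side.** Let *a* be the rise in the annual value and *m* the largest between-visit rise. A between-visit value creates a candidate when *a* fires the trigger, *a* does not itself exceed the loss threshold, and *m* does.

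- Liver: 25% ≤ *a* ≤ 50% and *m* > 50%. The band is 25 percentage points wide.
- Kidney: 25% ≤ *a* ≤ 25% and *m* > 25%. The band is the single point 25%, and it is empty if the trigger is read as more than 25%.
- Missed in both organs: *a* < 25% with *m* above the threshold, because nothing is retrieved.

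**Step 2: illustrative size.** Assumptions, none taken from the documents: a stable participant; one analyte; baseline, annual and *k* between-visit values independent and log-normal with common log-SD *s*; no confounding; no adjudication.

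From annual values alone, with threshold ratio *T*: P = 1 − Φ( ln *T* / (*s*√2) ).

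- Liver, *s* = 0.15: ln 1.5 = 0.4055; 0.4055 / 0.2121 = 1.911; P = 2.8%.
- Kidney, *s* = 0.15: ln 1.25 = 0.2231; 0.2231 / 0.2121 = 1.052; P = 14.6%.

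Retrieval adds P( ln 1.25 ≤ annual log-ratio ≤ ln *T*, and at least one of *k* between-visit log-ratios > ln *T* ), integrated over the shared baseline value. With *T* = 1.25 this term is zero.

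| Log-SD | Liver, annual only | Liver, 3 between-visit labs | Liver, 11 between-visit labs | Kidney, any number |
|---|---|---|---|---|
| 0.10 | 0.2% | 0.45% | 0.9% | 5.7% |
| 0.15 | 2.8% | 5.2% | 8.0% | 14.6% |
| 0.20 | 7.6% | 12.3% | 16.4% | 21.5% |

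At SD 0.15 retrieval adds 5.2 − 2.8 = 2.4 points with 3 labs and 8.0 − 2.8 = 5.2 points with 11. If creatinine varies less than the liver tests, the kidney total falls: it is 0.1% at SD 0.05.

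Using one analyte leaves out part of the liver rule, which tests both ALT and GGT; a rise in either one opens all liver tests.

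**Step 3: allowing for confounded annual values.** A creatinine more than 25% up but judged confounded still fires the trigger, and an unconfounded between-visit value can then create a kidney event. This was simulated with 2 or 4 between-visit labs a year, liver SD 0.15 to 0.35 and kidney SD 0.05 to 0.15 (all assumed). The table gives the share of detected laboratory losses that between-visit values created.

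| Annual values discounted as confounded | Liver | Kidney |
|---|---|---|
| None | about 20–51% | 0% |
| 10–20% | about 26–59% | about 1–15% |

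The kidney route exists, but it is much the smaller one.

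**The case against.** **Adjudication comes first.** The committee sees the plotted series, every relevant value, medication, rejection and biliary information, and then decides tolerance status. An isolated spike followed by an annual value under 50% would be visible to it. This stands: the percentages above are rates of candidates, not of endpoint events. But the committee's stated task is to look for confounding. It is not asked to even out how values were found, and a participant whose between-visit values were never retrieved cannot reach it by that route.

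**The affected analysis is modest.** The organ subsets are descriptive, there is no test or sample-size target, and accrual is estimated at about 70. This limits the importance of the point, but the curves will still be compared by eye.

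**A reader might infer that liver recipients are over-counted overall.** The documents do not support that. In the illustration the kidney total is the higher one at every common SD, and at a sufficiently low kidney SD it is the lower one. The documents give no variability for either organ.

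**A reader might also infer that between-visit creatinines can never create a kidney loss.** The confounded annual value and the exact 25% rise show otherwise.

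**A rule based on scheduled visits alone does not equalise detection.** Take as benchmark the losses that would be found if all between-visit labs were collected, with 4 such labs and SD 0.15. The current rule captures about 56% in liver and 37.5% in kidney; requiring an abnormal annual value gives about 28% and 37.5%. This stands, and it is why such an analysis should accompany the main organ curves and not replace them.

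**Conclusion.** The point holds in a limited form. The laboratory component of loss is ascertained by different effective rules in the two organs: retrieval can add candidates in liver and, apart from two narrow exceptions, only re-dates losses in kidney. This follows from the plan's own 25%, 50% and 25% figures and needs no assumption.

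The size does rest on assumptions. Across log-SDs of 0.10 to 0.20, retrieval with 3 to 11 between-visit labs adds between about 0.2 points (0.45 − 0.2) and 8.8 points (16.4 − 7.6) a year to the liver false-candidate rate before adjudication, and nothing to the kidney rate when annual values are unconfounded. Correlation between successive values, real graft decline and the committee's decisions would all change these figures.

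The net direction of any liver–kidney difference is not established. The point matters for how descriptive curves are read, and does not invalidate the primary analysis of the whole cohort.

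**What to change.** 1. In SAP 7.2.3, add a sensitivity analysis in which functional loss in both organs requires an unconfounded abnormal value at a scheduled annual visit, with between-visit values used only for dating.
2. Report, by organ, how many adjudicated functional losses rest on between-visit values alone. If there are none, the concern is settled.
3. In SAP 7.4, show this analysis beside the main organ-specific curves, and state that the differing thresholds still limit comparison of the laboratory component.

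The cost is one additional run on data already held, plus a record for each adjudicated case of which value the decision rested on. The drawback is that true losses seen only between visits drop out of the sensitivity analysis; they remain in the main one. No endpoint threshold or clinical procedure changes.

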### **Donor**

- Donor type (living-related donor, living-unrelated donor, deceased-donor)
- Demographics
- HLA and blood typing (if available)

## **6.3 CLINICAL LABORATORY ASSESSMENTS**

These laboratory assessments may be performed at study sites, at local laboratories, or through the central laboratory:

- Hematology – CBC with differential and platelets
- Comprehensive Metabolic Panel (Na, K, Cl, HCO3, BUN, creatinine, calcium, glucose, albumin, total bilirubin, direct bilirubin, GGT, AST, ALT, and alkaline phosphatase)
  - Screening allograft function tests must be obtained in the absence of confounding factors such as dehydration, infection etc. Abnormal test results should be repeated to confirm eligibility after any confounding conditions have resolved.
- Fasting lipid panel
- Urine albumin-creatinine ratio
- Urinalysis (protein, glucose, WBC, and hematuria)

## **6.4 MECHANISTIC ASSESSMENTS**

- Frozen PBMC – flow cytometry panel staining
- Frozen PBMC – cellular assays
- Serum – HLA alloantibodies, includes DSA, flow PRA
- Whole Blood – RNA gene expression profiling
- Urine pellet – gene expression profiling (not indicated for remote visits)

- Fecal – microbiome profiling

See section 7 for detailed discussion of additional mechanistic assays.

## 7. TOLERANCE ASSAYS

### 7.1 MECHANISTIC STUDIES

The aim of this trial is to create a repository for samples obtained from operationally tolerant transplant recipients that have either completed ITN studies or have otherwise successfully withdrawn from immunosuppressive therapy. These samples will allow the ITN to longitudinally assess the phenotype, maintenance, generation, and stability of immune transplant tolerance in both kidney and liver transplant recipients. In addition, mechanistic data and samples collected from ALLTOL participants during previous ITN studies may be used to supplement the ALLTOL specimens and data, as needed.

We propose to monitor related parameters over time and collect blood, cells, serum, urine, urine pellet, and fecal microbiome samples from tolerant participants. As the field of tolerance is evolving, markers of interest will be determined based on the literature and state-of-the-art at the time of experimentation.

### 7.2 FUTURE / UNPLANNED STUDIES

Exploratory ancillary studies may be performed at a future date. Appropriate comparator arms will be determined at the time of experimentation and may include comparison with previously banked specimens or recruitment of control participants. Participants will be consented for sample storage and future use. Specimens stored during the trial may also be used in future assays to reevaluate biological responses as research tests are developed over time. Additionally, samples may be used for assays/ experiments outside the scope of this proposal, such investigation of miRNA expression, differences in the TCR repertoire as evaluated by sequencing, proteomics or other explorations that may emerge and be compelling during the trial period. Reevaluations or new assays will only be performed on samples of participants who have consented for future research. Blood samples will be collected and saved to allow for the possible use in later gene association studies. Specific consent will be obtained for the storage and use of participant DNA. The ITN sample sharing policy will apply for the provision of samples to study or outside investigators.

### 7.3 SPECIMEN LOGISTICS

Sites will be trained in the collection, processing, shipment, and tracking of mechanistic research specimens. The ITN will monitor specimen quality, shipping compliance, etc., and retrain any clinical site that is not producing optimum quality mechanistic samples. Sites will process all mechanistic samples according to the ITN standard procedures and use the ITN Specimen Tracking System (STS) software to identify and track all mechanistic specimens. The sites will be required to have certain laboratory equipment for use in following ITN procedures, such as a centrifuge for spinning primary blood tubes, a micropipettor to aliquot specimens, and freezer to store frozen specimens until they can be shipped. Sites will use appropriate courier service for shipping specimens to repositories/ core labs, per ITN standard procedures. All shipping will

conform to Department of Transportation regulations (49 CFR 173.199) for Diagnostic Specimens.

If samples cannot be collected at the study site, the site study coordinator will arrange for a representative from an ITN approved vendor to come to the participant's location to complete the study assessments. The ITN approved vendor will be trained in the ITN standard procedures for collection, processing and shipment of mechanistic research specimens. The site study coordinator(s) will use the ITN Specimen Tracking System (STS) software to identify and track all mechanistic specimens.

### **7.3.1 Specimen Tracking Procedures**

The ITN will track all mechanistic specimens until the final disposition of all material is known. Samples will remain in the ITN repository until used for assays or destroyed.

### **7.3.2 Sample Storage**

Samples sent to the ITN repository will be stored under specific conditions to maintain long-term sample integrity, as well as specimen tracking from receipt to shipment to alternate locations. A 21 CFR Part 11 validated database system can be used to track shipment date, location shipped to, carrier, items shipped, amount shipped, barcode numbers, protocol number, and associated comments about each individual specimen. Storage temperature, location, processing and aliquoting, and freeze/thaw events may also be recorded.

If the study participant allows storage, the participant's specimens will be stored indefinitely. The participant can change their mind at any time and have their stored specimens destroyed by notifying the study physician in writing. In such cases, the site coordinator would send all requests for sample destruction to the ITN. The site will receive confirmation that the specimen was destroyed as requested. If the participant's samples have already been analyzed, then the data will be used as part of the overall analysis. The participant can only request to have samples destroyed if they still exist, i.e. have not already been used in an experiment.

Specimens at the ITN core or repository can only be transferred to another destination with appropriate authorization per ITN standard procedures. Purpose for accessing/transferring the specimen (within study assay as defined by the protocol or future studies), evaluation of participant consent for the purpose provided, verification of specimen identifiers, and quality and quantity of the specimen are some of the items checked prior to authorization.

If the purpose is for future studies, and the participant consents for storage for future use, the participant's sample may be made available to the scientific research community per the ITN Sample Sharing Policy [REDACTED]. Any research conducted using stored samples for future use may also need appropriate regulatory approval, such as Institutional Review Board per the study consent.

